5. INTRODUCTION

TNX-102 SL is a tablet for sublingual administration containing cyclobenzaprine HCl [3-(5H-dibenzo[a,d]cyclohepten-5-ylidene)-N,N-dimethyl-1-propanamine hydrochloride]. TNX-102 SL 2.8 mg tablets are under development by Tonix Pharmaceuticals, Inc. (Tonix) as a treatment for posttraumatic stress disorder (PTSD).

The active ingredient in TNX-102 SL, cyclobenzaprine HCl (CBP), has been approved for use in the United States (US) since 1977, originally as FLEXERIL[®] 10-mg oral tablets indicated as an adjunct to rest and physical therapy for the relief of muscle spasm associated with acute, painful musculoskeletal conditions. The usual dose for this indication is 30 mg or 15 mg per day taken as 10 mg TID or 5 mg TID, respectively. The FLEXERIL brand of immediate-release (IR) cyclobenzaprine tablets has been discontinued since May 2013. Generic cyclobenzaprine is available and marketed in a variety of strengths including 5-, 7.5- and 10-mg IR tablets.

AMRIX[®] (AMRIX[®] Prescribing Information, 2016), an extended-release capsule of cyclobenzaprine was approved in 2007 in the US as a New Drug Applications (NDA) and is currently available in 15- and 30-mg, taken once a day for the same indication as FLEXERIL in the US. Both FLEXERIL and AMRIX are indicated for 2-3 weeks use only. No cyclobenzaprine product has been approved for use in PTSD by Food and Drug Administration (FDA), Health Canada, or in any other country.

As its primary pharmacologic action in relief of muscle spasm, cyclobenzaprine has been shown to decrease skeletal muscle hyperactivity in several animal models through central mechanisms involving blockade of either α_2 -adrenoreceptors (Barnes et al, 1980) (AR) or serotonergic 5-HT_{2A} receptors (Kobayashi et al, 1996; Honda et al, 2003). Cyclobenzaprine acts primarily in the central nervous system (CNS) at the brain stem rather than at the spinal cord level, and does not act directly at the neuromuscular junction or directly on skeletal muscle.

In addition to these primary pharmacologic actions, cyclobenzaprine has been observed to increase restorative sleep in fibromyalgia patients, which was correlated with improvement in daytime symptoms in a proof-of-concept study conducted by Vela Pharmaceuticals (Protocol No. VPI CY 0001.1) (Moldofsky et al, 2011) using low dose cyclobenzaprine (TNX-102 capsules). The rationale for testing cyclobenzaprine as a treatment for PTSD is based on known effects of cyclobenzaprine on CNS receptors and, in part, on the relationship of fibromyalgia and PTSD to disturbed and non-restorative sleep.

PTSD is characterized by symptom clusters that include re-experiencing (intrusion) symptoms, avoidant behaviors, negative mood and cognitions, and heightened arousal and reactivity, the array of which develops and persists following exposure to a severely traumatic event. It is well established that sleep disturbances are common among individuals with PTSD that has developed in response to combat traumas (Mellman et al, 1995; Pietrzak et al, 2010; Neylan et al, 1998) and sexual assault (Steine et al, 2012), including military sexual trauma (Kelly et al, 2011). Among military personnel returning from OEF/OIF/OND deployments to Afghanistan and Iraq, sleep disturbances are considered the most frequent and severe of the PTSD symptoms (McLay et al, 2010). Sleep disturbances are considered core features of PTSD and are components of two of the main symptom clusters of PTSD including distressing dreams (re-experiencing cluster) and insomnia and restless sleep (hyperarousal cluster) (Krakow et al, 2001; Spoomaker et al, 2008). Problems with sleep are not only thought to significantly exacerbate

daytime symptoms of PTSD but also increase the likelihood of comorbid complications such as depression and substance use disorders as well as suicidal behaviors (Krakow et al, 2002; Saladin et al, 1995; Krakow et al, 2000), a particularly critical problem in PTSD (Oquendo et al, 2003; Sareen et al, 2005). Moreover, because of a direct relationship between sleep disturbance in PTSD and suicidal ideation, it is suggested that targeting sleep disturbance may help prevent suicidal behaviors in PTSD (Betts et al, 2013).

A growing body of evidence suggests that sleep disruption plays an important causal role in the pathogenesis of PTSD (Koren et al, 2002; Mellman et al, 2002; McLay et al, 2010; Wright et al, 2011). Moreover, sleep disturbance is a frequent residual complaint after successful PTSD treatment, a finding that applies to both psychological and pharmacological treatment (Spoormaker et al, 2008). Evidence is now emerging that pharmacological targeting of sleep disturbance in PTSD, in which self-reported and polysomnographic improvement in sleep parameters is achieved, can account for over 90% of the variance in improvement in PTSD severity ratings and work/school function (Krystal et al, 2013).

Understanding of PTSD pathophysiology has been greatly advanced due to heuristic models of trauma based on animal work on fear conditioning and extinction (Yehuda & LeDoux, 2007; Maren et al, 2013). Human studies of fear memory and stress responsiveness have highlighted the potential role of sleep, particularly rapid eye movement (REM) sleep, in affective and memory processes (Pace-Schott et al, 2015; Yoo et al, 2007; Pace-Schott et al, 2009). There is evidence for the hypothesis that sleep disturbances play a critical role in PTSD by compromising sleep-dependent affective and memory processing that may be key for recovery from PTSD (Yehuda & LeDoux, 2007).

5.1. Sleep and PTSD

Subjective sleep disturbance, characterized by non-restorative sleep, frequent awakenings and distressing dreams and nightmares related to the trauma, is a core feature of PTSD (Spoormaker et al, 2008). Clinical observations focusing on the nature of sleep complaints suggest dysregulation in both REM and non-rapid eye movement (NREM) sleep in PTSD (Woodward et al, 2000; Germain et al, 2013). Meta-analysis of polysomnography (PSG) studies in both military veterans and adult civilians suggest modest indices of sleep disruption in PTSD using these traditional measures, with greater stage 1 (light) sleep, reduced slow wave sleep (SWS), and greater REM density compared with individuals without PTSD (Kobayashi et al, 2007). Quantitative EEG, in which high frequency beta and gamma activity are considered indices of central arousal during sleep, has indicated both greater beta activity during NREM and lesser beta activity during REM sleep in PTSD, as well as disturbances in delta activity, and heart rate differences between REM and NREM related to the amount of REM sleep (Woodward et al, 2002; Neylan et al, 2003; Halász et al, 2004; Woodward et al, 2000). Such changes are consistent with the pathophysiology of PTSD, which involves hypervigilance and exaggerated responses to both external and internal stimuli, and which are putatively indicative of heightened nocturnal sympathetic noradrenergic activity (Berridge et al, 2012; Breslau et al, 2005; Capaldi et al, 2011).

A recent evaluation of treatment algorithms for PTSD found that addressing fragmented sleep and nightmares consistently improves all symptom domains in PTSD, such that targeting sleep-related symptoms has been recommended as an initial step for treatment of all patients with

PTSD (Bajor et al, 2011). Prazosin, a centrally acting α_1 -adrenoreceptor antagonist, has been repeatedly demonstrated to provide improvements on subjective measures of sleep disturbance and PSG in both civilian and combat related trauma (Raskind et al, 2003; Taylor et al, 2008; Raskind et al, 2007; Raskind et al, 2013). It is notable that prazosin treatment has also been reported to improve non-sleep symptoms in PTSD (Taylor et al, 2006; Raskind et al, 2007), however, a recently reported large (N=304) multicenter VA cooperative study (#563) failed to show improvement on total CAPS score with prazosin (<https://clinicaltrials.gov/ct2/show/results/NCT00532493>).

Normal NREM sleep is associated with a reduction in sympathetic nervous system drive and increase in parasympathetic nervous system drive (Berridge et al, 2012; Pace-Schott et al, 2015). In PTSD, there is evidence that the nocturnal secretion of norepinephrine remains high, which could be a factor resulting in fragmented REM sleep. Since cyclobenzaprine shares α_1 -adrenoreceptor antagonist activity with prazosin, cyclobenzaprine may have similar therapeutic effects on sleep disturbances in PTSD based on this molecular target.

In addition to the efficacy evidence demonstrated in the TNX-102 SL Phase 2 study (Section 5.1.1), the potential clinical utility of cyclobenzaprine in treating PTSD is also supported by the promising results of studies with agents that share a molecular mechanism of antagonism of the 5-HT_{2A} receptor (Hertzberg et al, 1996; Warner et al, 2001; Davidson et al, 1998; Hertzberg et al, 1998; Hidalgo et al, 1999; Davis et al, 2004; Connor et al, 1999; Bahk et al, 2002; Kim et al, 2005; Lewis, 2002; Davidson et al, 2003). The 5-HT_{2A} blocking activity of cyclobenzaprine may be crucial to the aforementioned enhancement of sleep-dependent memory processing believed to be necessary for recovery from PTSD (Datta & O'Malley 2013; Karshima et al, 2010; Siwek et al, 2014; Data et al, 2008). Another of cyclobenzaprine's high affinity receptors, also where it acts as an antagonist, is the H₁ receptor, which has been shown to have antianxiety effects (Llorca et al, 2002), play a role in wake promotion (Monti et al 2011; Huang et al, 2006), and has been implicated in emotional processing (Serafim et al, 2012, 2013) known to be sleep-dependent. Thus, in summary, the pharmacodynamic profile of cyclobenzaprine's CNS receptor activities appears well-suited for treating PTSD based on its potential to combine the activities on sleep and emotional memory processing of the α_1 -adrenergic receptor antagonist prazosin, 5-HT_{2A} receptor antagonist antidepressants, and histaminergic H₁ antagonists.

5.1.1. Brief Summary of Prior Clinical Experience and Dose Rationale

[REDACTED]

[REDACTED]

[REDACTED]

[REDACTED]

[REDACTED]

[REDACTED]

[REDACTED]

[REDACTED]

[REDACTED]

[REDACTED]

[REDACTED]

[REDACTED]

[REDACTED]

[REDACTED]

6. TRIAL OBJECTIVES AND PURPOSE

6.1. Primary Objective

To evaluate the efficacy of TNX-102 SL (cyclobenzaprine HCl sublingual tablets) in the treatment of military-related PTSD.

6.2. Secondary Objectives

To evaluate the safety of TNX-102 SL (cyclobenzaprine HCl sublingual tablets) in the treatment of military-related PTSD.

7. INVESTIGATIONAL PLAN

7.1. Overall Study Design

This is a Phase 3, 12-week, randomized, multicenter, double-blind, placebo-controlled, fixed dose study that will investigate the efficacy and safety of TNX-102 SL 5.6 mg (2 x 2.8 mg tablets) taken daily at bedtime for the management of military-related PTSD. This study is to be conducted at approximately 45 investigational sites in the United States.

The total duration of this study over 6 visits will be approximately 13-17 weeks, with 12 weeks of treatment duration and a variable length of screening. This study will consist of a Screening visit (Visit 1, Days -35 to -8), Randomization visit (Visit 2, Day 0), telephone visit (Visit 3, Week 2) and three monthly in-clinic visits (Visits 4, 5 and 6 at Weeks 4, 8, and 12).

Eligible patients who provide written informed consent to participate will have study assessments performed at Screening, including counseling regarding any required washout and instructions to refrain from use of excluded medications throughout the study.

The length of the pre-randomization screening period is variable (7 to 35 days) in order to accomplish wash-out of previous medications, where appropriate, and allow for return of clinical laboratory results necessary to confirm eligibility. At Visit 2, patients will return to the site for additional baseline assessments and randomization (Day 0), when, if they meet all study randomization criteria, they will be randomly assigned in a 1:1 ratio to receive placebo or TNX-102 SL 5.6 mg. Patients will take the study drug sublingually daily at bedtime, starting on the day that they are randomized and continuing for 12 weeks (or to early termination). A dynamic randomization procedure will be employed at Visit 2 to minimize trial-wide imbalances between the treatment groups for site, sex, current tobacco/nicotine use (yes/no) and presence (yes/no) of current Major Depressive Episode (MDE) based on the Mini International Neuropsychiatric Interview, Version 7.0.2 (M.I.N.I. 7.0.2) conducted at Visit 1.

Patients who test positive for cocaine, ecstasy (MDMA), methamphetamine or other non-disclosed illicit drugs (other than marijuana) should be screen-failed. In addition, patients who meet M.I.N.I. criteria outlined in the entry criteria for alcohol/substance use disorder over the 6 months prior to Screening should be screen-failed.

Patients suffering from depression are eligible for the study, provided their depression does not pose an undue risk to their well-being (e.g., suicidal risk) or warrant treatment with

antidepressants or other excluded treatments. The investigator will evaluate each patient's medical and psychiatric history, current symptomatology, and the results of the MINI 7.0.2, BDI-II, C-SSRS, and CAPS-5 from Visits 1 and 2, to determine whether it is appropriate for the patient to participate in the study. In addition, each patient will undergo medical monitor pre-randomization review to ensure agreement with the investigator's assessment.

NOTE: Patients who use alcohol/marijuana but do not meet criteria for alcohol/substance use disorder (per Diagnostic and Statistical Manual of Mental Disorders [Version 5; DSM-5]) are otherwise suitable for the study provided that, in the judgment of the Investigator, this usage will not interfere with the patient's ability to complete the study or provide reliable data. Information related to marijuana and alcohol use will be collected at Screening.

Patients with evidence of hepatic impairment secondary to hepatitis B or C at screening, or who are undergoing treatment for hepatitis, should be excluded. Patients with stable and asymptomatic disease whose hepatic enzymes (aspartate aminotransferase [AST] or alanine aminotransferase [ALT]) satisfy the study's entry criteria (< 3 times the upper limits of normal), may be allowed to proceed with randomization with prior Medical Monitor approval.

CAPS-5, M.I.N.I. 7.0.2 and Columbia Suicide Severity Rating Scale (C-SSRS) interviews will be conducted by an approved and qualified individual(s) at each site who has successfully completed training on each instrument.

If a patient scores a 2 or 3 on the suicidal ideation section of the C-SSRS at any visit (including the Screening visit), the investigator and patient should work together to implement a Safety Planning Intervention (SPI). As described in detail in [Section 11.3.3](#), the recommended SPI for this study is the plan developed by [name] and [name] which has been adopted by the U.S. Veteran's Administration (VA) ([Stanley & Brown, 2012](#)). The VA SPI is a brief clinical intervention aimed at mitigating suicide risk. It consists of a written, prioritized list of coping strategies and sources of support that patients can use to alleviate a suicidal crisis. Sites may use an internally-developed SPI if similar in scope and purpose to the VA SPI.

The study timeline and events schedule is provided in [Appendix 1](#).

7.2. Number of Patients and Treatment Assignment

A total of approximately 550 patients will be randomized in a 1:1 ratio to treatment with TNX-102 SL 5.6 mg (2 x 2.8 mg) tablets or identical SL placebo tablets. See [Section 13.2](#) for details regarding potential sample size adjustment.

7.3. Study Endpoints

7.3.1. Primary efficacy endpoint

The primary efficacy endpoint will be the mean change from baseline in the total Clinician Administered PTSD Scale-Version 5 (CAPS-5) at Week 12.

7.3.2. Secondary efficacy endpoints

7.3.2.1. Key Secondary Efficacy Endpoints

The first two secondary efficacy endpoints listed below are considered key secondary endpoints and will be tested in that order:

- CGI-I score (analyzed as a continuous variable) after 12 weeks of treatment.
- Change from baseline in the SDS total score after 12 weeks of treatment.

A fixed sequence procedure will be applied to the key secondary efficacy endpoints to adjust for multiplicity and to control for overall type I error.

7.3.2.2. Other Secondary Efficacy Endpoints

- Change from baseline in patients' quality of sleep using the PROMIS Sleep Disturbance scale after 12 weeks of treatment.
- Change from baseline in the disruption of work/school activities assessed using the SDS after 12 weeks of treatment.
- Change from baseline in disruption of social life/ leisure activities assessed using the SDS after 12 weeks of treatment.
- Change from Baseline in the disruption of family life/home responsibilities assessed using the SDS after 12 weeks of treatment.
- Change from baseline in CAPS-5 Arousal and Reactivity (Criterion E) score after 12 weeks of treatment.
- Change from baseline in CAPS-5 Intrusion symptoms (Criterion B) score after 12 weeks of treatment.
- Change from baseline in CAPS-5 Persistent Avoidance (Criterion C) score after 12 weeks of treatment.
- Change from baseline in CAPS-5 Negative Cognition and Mood (Criterion D) score after 12 weeks of treatment.
- Change from baseline in CAPS-5 Sleep Disturbance (item E-6) score after 12 weeks of treatment.
- Change from baseline in CAPS-5 Exaggerated Startle (item E-4) score after 12 weeks of treatment.
- PGIC score after 12 weeks of treatment.
- Proportion of patients with a PGIC score of "much improved" or "very much improved" after 12 weeks of treatment
- Proportion of patients with a treatment response on the CGI-I defined as a CGI-I score of "much improved" or "very much improved" after 12 weeks of treatment.
- Proportion of patients with a Total CAPS-5 score of 0 –10 (asymptomatic/few symptoms) after 12 weeks of treatment.

- Proportion of patients with a Total CAPS-5 score of 0-22 (asymptomatic or mild PTSD/subthreshold) after 12 weeks of treatment.
- Proportion of patients with Response, defined as a ≥ 10 -point improvement from baseline in Total CAPS-5 score after 12 weeks of treatment.
- Proportion of patients with Loss of Diagnosis, defined as Response AND no longer meeting DSM-5 symptom criteria in any one or more of the four clusters (B, C, D, E) after 12 weeks of treatment.
- Proportion of patients in Remission, defined as Loss of Diagnosis AND Total CAPS-5 score ≤ 10 after 12 weeks of treatment.
- Proportion of patients achieving sustained Remission, defined as Loss of Diagnosis AND Total CAPS-5 score ≤ 10 after both 8 weeks AND 12 weeks of treatment.
- Proportion of patients with a $\geq 50\%$ improvement from baseline in Total CAPS-5 score after 12 weeks of treatment.
- Change from baseline in BDI-II score after 12 weeks of treatment.
- Change from baseline in CAPS-5 Reckless or Self-Destructive Behavior (item E-2) score after 12 weeks of treatment.

7.3.3. Exploratory efficacy endpoints

Any exploratory endpoints will be delineated in the SAP.

7.3.4. Safety

Safety will be assessed by:

- Adverse events (AE) and serious AEs (SAEs) throughout the entire duration of the study, including detailed assessment of AEs involving the oral cavity
- Changes from baseline in clinical laboratory test results
- Changes from baseline in vital signs and weight
- Change from baseline in BDI-II
- Changes from baseline indicative of increased suicidal ideation or behavior as assessed by the Columbia Suicide Severity Rating Scale (C-SSRS)
- Changes from baseline in patient-rated Changes in Sexual Functioning Questionnaire Short-Form (CSFQ-14)
- Changes from baseline in patient-rated morning sedation as assessed by the Morning Treatment-Related Sedation Score (MTRSS)

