The Changes in Sexual Functioning Questionnaire Short-Form (CSFQ-14) (Keller et al. 2006) is a validated scale with internal reliability designed to allow a patient to self-evaluate his or her sexual behaviors or problems in a number of areas. The CSFQ-14 will be administered at Baseline (Visit 2) and Week 12/ET (Visit 6). It yields a total score, three subscales corresponding to phases of the sexual response cycle (i.e. desire, arousal, orgasm), and five subscales corresponding to important dimensions of sexual functioning. It is considered a useful scale for assessing sexual side effects of medications. For all items, higher scores reflect higher sexual functioning. For 12 of the 14 items, higher sexual functioning corresponds to greater

frequency or enjoyment/pleasure (e.g. 1=never to 5 = every day). For two items (item 10, assessing loss of interest after arousal for women and priapism for men, and item 14, assessing painful orgasm), higher sexual functioning corresponds to lower frequency (e.g. 1=every day to 5=never). Items 10 and 14 are included in the total score but not in any scale score.

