13.5. Safety Analyses

Safety will be assessed by:

- Adverse events and serious AEs throughout the entire duration of the study, including assessment of AEs involving the oral cavity

- Changes from baseline in clinical laboratory test results
- Changes from baseline in vital signs and weight
- Changes from baseline indicative of increased suicidal ideation or behavior as assessed by the C-SSRS
- Changes from baseline in BDI-II
- Changes from baseline in patient-rated sexual function as assessed by the CSFQ-14
- Changes from baseline in patient-rated morning sedation as assessed by the MTRSS

Adverse events will be coded using the latest version of MedDRA and will be summarized overall and by preferred term and system organ class. Adverse events will also be summarized by severity and relationship to study drug. Serious AEs and AEs leading to discontinuation of study drug will also be summarized. Actual values and changes from Baseline for clinical laboratory test results, MTRSS scores, CSFQ-14 scores, BDI-II scores, and vital sign measurements will be summarized at endpoint using descriptive statistics (n, mean, SD, median, minimum, and maximum).

The number of patients with suicidal behaviors, ideations and acts based on the C-SSRS will be tabulated by treatment group and listed.

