## **7. GENERAL ISSUES FOR STATISTICAL ANALYSIS**

### **7.1 General Statistical Methodology**

Descriptive summaries will be provided where appropriate for each of the primary and secondary variables. In general, tables will summarize data by treatment group and visit.

Baseline characteristic and safety tables will be completed for the Safety Population unless otherwise specified. Efficacy tables will be presented for the mITT Population.

Continuous, quantitative, variable summaries will include the number of participants (N) with non-missing values, mean, standard deviation (SD), median, minimum, and maximum.

Categorical, qualitative, variable summaries will include the frequency and percentage of participants who are in the particular category. In general, the denominator for the percentage calculation will be based upon the total number of participants in the study population for the treatment group unless otherwise specified.

Baseline values are defined as the last non-missing measurement prior to the first dose of study drug. Change from baseline will be defined as the post-baseline visit value minus the baseline value.

ET participants will only be followed if required to monitor an on-going adverse event or other condition.

Participants are not supposed to change study sites; however, should this be necessary to allow a participant to continue in the study, participants will be analyzed under the site where they were initially enrolled.

Study day after first dose is defined as assessment date – first dose date +1. Dates prior to first dose are defined as assessment date – first dose date. Note that the protocol refers to “Day 0”; for the purposes of the datasets and analyses, this would appear as day 1.

All analyses will be performed using Statistical Analysis System (SAS®) Software version 9.3 or later.

Alpha levels are discussed in [Section 7.1.1.2](#) below; unless otherwise noted, 95% confidence intervals will be presented for statistical tests.

Presence of current tobacco/nicotine use and MDE is recorded first in the Interactive Web Response System (IWRS) during screening for purposes of randomization stratification and, after randomization, transcribed into the electronic data capture (EDC) system (as part of substance use history and the results for the MINI). The source for tobacco/nicotine use MDE in all analyses and statistical models will be the EDC data and not the IWRS.

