### **10.8 Assessment of Changes in Sexual Function: Changes in Sexual Functioning Questionnaire Short-Form (CSFQ-14)**

The CSFQ-14 ([Keller et al. 2006](#)) is a validated scale with internal reliability designed to allow a participant to self-evaluate his or her sexual behaviors or problems in several areas. The CSFQ-14 will be administered at Baseline (Visit 2) and Week 12/ET (Visit 6). It yields a total score, three subscales corresponding to phases of the sexual response cycle (i.e. desire, arousal, orgasm), and five subscales corresponding to important dimensions of sexual functioning. It is considered a useful scale for assessing sexual side effects of medications. For all items, higher scores reflect higher sexual functioning. For

12 of the 14 items, higher sexual functioning corresponds to greater frequency or enjoyment/pleasure (e.g. 1=never to 5 = every day). For two items (item 10, assessing loss of interest after arousal for women and priapism for men, and item 14, assessing painful orgasm), higher sexual functioning corresponds to lower frequency (e.g. 1=every day to 5=never). Items 10 and 14 are included in the total score but not in any scale score.

Descriptive summaries (mean, SD, median, minimum, and maximum) of actual values and changes from baseline at each assessment time point will be reported.

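### CSFQ-14 is summarized without regard to sex, although item 10 in its total score measures a different symptom in men and in women

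*Protocol*

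**What the plan says.** CSFQ-14 change is a listed safety measure: "Changes from baseline in patient-rated Changes in Sexual Functioning Questionnaire Short-Form (CSFQ-14") (Protocol 7.3.4, repeated in SAP 2.2.3).

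Protocol 11.3.9 and SAP 10.8 describe the instrument in near-identical terms. Item 10 is sex-dependent: "item 10, assessing loss of interest after arousal for women and priapism for men". On scoring: "Items 10 and 14 are included in the total score but not in any scale score". On direction: "For all items, higher scores reflect higher sexual functioning".

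The analysis is descriptive:

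- SAP 10.8: "Descriptive summaries (mean, SD, median, minimum, and maximum) of actual values and changes from baseline at each assessment time point will be reported". It does not mention sex, and it does not say whether the total, the subscales or both are tabulated.
- Protocol 13.5: CSFQ-14 and other measures "will be summarized at endpoint using descriptive statistics (n, mean, SD, median, minimum, and maximum").
- SAP 7.1, on default layout: "In general, tables will summarize data by treatment group and visit".

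No safety summary in either document is planned by sex. Sex is otherwise used as a covariate in the efficacy models (SAP 9.1.1), as a baseline characteristic, and in treatment allocation, which is designed to "minimize trial-wide imbalances between the treatment groups for site, sex, current tobacco/nicotine use" and current MDE (Protocol 7.1).

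**The concern.** The plan describes an instrument that depends on sex and then leaves sex out of its summary. There are two separate consequences.

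1. **Interpretation of the total.** One component of the total is priapism in men and loss of interest in women. Because that component is in no subscale, no subscale table can recover it. If the total moves, the planned summary tables cannot say which symptom, if either, contributed.
2. **Dilution.** When both sexes are pooled, an effect on any item that occurs in one sex only is multiplied by that sex's share of the patients. For a minority sex little of it may remain.

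A one-sex effect is plausible on the sponsor's own material. The cyclobenzaprine package insert in Protocol Appendix 3 lists several urogenital and breast-related reactions, some of them specific to one sex, as reported with cyclobenzaprine or with other tricyclics. The CSFQ-14 is also the only structured questionnaire on sexual function in the trial. Adverse events are elicited with general, non-leading questions (Protocol 11.3.1), so a graded decline in function may never be reported as an event.

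**Working it through.** The documents give no CSFQ-14 figure to reproduce, so this is an illustration of size.

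**Inputs from the documents**
- 275 patients per arm, 1:1 (SAP 5).
- 14 items; the response scale is given by example as 1 to 5 (Protocol 11.3.9).

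**Assumptions (not in the documents)**
- Share *f* of the affected sex: 10–20% for a minority sex, hence 80–90% for the majority.
- SD of change in the total: 7 to 9 points, the same in both sexes.
- A 4-point worsening on drug in one sex, none in the other.
- All randomized patients evaluable.

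**Formulas**
- Pooled difference = *f* × 4.
- z pooled = *f* × 4 / (SD × √(2/275)), with √(2/275) = 0.0853. The slight inflation of the pooled SD is ignored.
- z within the affected sex = 4 / (SD × √(2/(275*f*))).

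The plan tests nothing on CSFQ-14. The z values only indicate how far a difference stands out from noise.

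| Share *f* | n per arm in that sex | Pooled difference | z pooled (SD 9 to 7) | z within sex (SD 9 to 7) |
|---|---|---|---|---|
| 10% | 27.5 | 0.4 | 0.52 to 0.67 | 1.65 to 2.12 |
| 20% | 55 | 0.8 | 1.04 to 1.34 | 2.33 to 3.00 |
| 80% | 220 | 3.2 | 4.17 to 5.36 | 4.66 to 5.99 |
| 90% | 247.5 | 3.6 | 4.69 to 6.03 | 4.94 to 6.36 |

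In every row z pooled / z within sex = √*f*: 0.32 and 0.45 for the minority rows, 0.89 and 0.95 for the majority rows. The loss is large only for a minority sex.

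**How much of this is item 10?** If every item runs 1 to 5, the total spans 14 × 4 = 56 points and item 10 spans 4, or 4/56 = 7.1%. If 10% of one sex moved the whole length of item 10, the total in that sex would shift by 0.10 × 4 = 0.4 points. Pooled, that is 0.04–0.08 points at a 10–20% share and 0.32–0.36 points at 80–90%. The 4-point illustration therefore represents a general effect on the total. Item 10 alone would produce it only if the whole affected sex moved from one end of the item to the other.

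**Precision of the proposed display.** The 95% CI for mean change in one arm of the smaller sex has half-width 1.96 × SD/√n. That is 1.96 × 7/√55 = 1.9 points at best and 1.96 × 9/√27.5 = 3.4 points at worst.

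**The case against.** A good deal can be said for the plan as it stands, and most of it limits the point.

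- **Pooling is inferred.** SAP 10.8 never says the sexes are combined. This stands as a matter of wording. But the default layout is treatment by visit and sex is named nowhere in the safety analyses, so a programmer following the SAP would produce pooled tables.
- **Item 10 is a small part of the instrument.** It is 1 of 14 items, scored in the same direction for both sexes and outside every subscale. This stands: item 10 raises a problem of interpretation, while dilution applies to all items alike.
- **Other outputs exist.** Treatment-emergent events are tabulated by preferred term (SAP 10.1) and safety data are listed (SAP 10). A reported priapism would appear by name. This stands for reported events. It does not provide an arm comparison within sex, nor does it capture a decline that nobody reports.
- **The measure is descriptive and the subgroup small.** At a 10% share and SD 9, z within that sex is 1.65, so a by-sex table would not reliably reveal the effect either. An early stop, with about 275 patients in total (SAP 4.1), would roughly halve the numbers. This stands, and it argues against formal between-arm inference here. It does not argue against showing the data.

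A reader might go further and infer that any one-sex side effect would be averaged away. The documents do not support that. They give no expected sex split, and an effect in the majority sex keeps most of its size. Nor do they support the inference that the comparison of arms is distorted: sex is a minimization factor, so the arms should be similar in sex mix.

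**Conclusion.** The point holds in a limited form. Both documents state that item 10 differs by sex and enters the total only, and neither plans a summary by sex. Two consequences follow from the plan as written: a change in the total cannot be assigned to either symptom from the planned summary tables, and an effect confined to a minority sex is reduced to its share.

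The first consequence needs no assumption beyond the default layout. The second depends on the share. At an assumed 10–20%, 4 points become 0.4–0.8, with z of 0.5–1.3 pooled against 1.65–3.0 within that sex, assuming SD 7–9 and full evaluability. At 80–90% the same effect still shows as 3.2–3.6 points. The documents do not say which sex is the smaller or by how much.

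This concerns masking and interpretability of one descriptive safety measure. It does not bias the comparison between arms, and it does not mean that a one-sex effect must go unseen, because reported events have their own tables and listings. It is a cheap improvement to the SAP.

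**What to change.** In SAP 10.8:

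- State which CSFQ-14 scores are tabulated, namely the total and the subscales.
- Summarize actual values and changes from baseline descriptively by treatment arm within sex, at Baseline and Week 12/ET, with a 95% CI for change. The SAP already gives that interval for laboratory values (10.2) and vital signs (10.4).
- Show item 10 separately for men and for women, labelled with the symptom it measures in each.
- Keep the pooled table as a secondary display.

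No test is needed. The cost is SAP wording and one extra table, with no new data, visits or patients. The downside is imprecision in the smaller sex, and the table should carry its n so that readers do not over-interpret it.
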